11.2. General Statistical Considerations

All analyses will be performed on observed data only. No missing data will be imputed. Data on subjects who do not reach a specific endpoint will be censored in the corresponding statistical analyses.

Raw data will be presented with the exact precision (decimal points) with which it was collected.

The p-values will be presented in the end-of-text tables exactly as they are in supporting statistical documents (4 decimal points). The text and in-text tables will display p-values with three decimal places, as long as, the decision for statistical significance will not be changed by rounding.

The number of decimal places to display for calculated data will be determined by the scale of measurement. No decimal places will be displayed if the smallest calculated value is ≥ 100 ; One (1) decimal place will be displayed when all calculated values are within the interval (10, 100), with 10 being inclusive; Two (2) decimal places will be displayed when all calculated values are within (1, 10), with 1 being inclusive; and so on for even smaller scales of measurement. Percentages will be reported with exactly one decimal place.

For continuous variables, statistical summaries will include n (number of subjects with non-missing data), mean, median, standard deviation, minimum and maximum: Means and medians will be displayed to one more decimal places than the raw or calculated data; standard deviation and other dispersion statistics will have two more decimal places; and minimum and maximum values will be displayed to the same number of decimal places as the raw or calculated data.

For categorical variables, statistical summaries will include counts and percentages. Percentages will be reported with exactly one decimal place. In general, percentages are based on the total number of subjects with information available (ie non-missing data). For AE and incidence based analyses, percentages will be based on the total number of subjects in the analysis set of interest and in that treatment regimen.

The statistical data analysis will be performed by a CRO under the guidance of the study biostatistician using SAS Version 9.3 or higher.

Definition of terms:

'Overall Study Period': This period is defined as the time from the reference date (date and time of randomization or date and time of first study edoxaban or study VKA intake) to Day 365.

'Overall Study Period = 30 days': This period is defined as the time from the reference data (date and time of randomization or date and time of first study edoxaban or study VKA intake) to Day 395.

'Initial dose to Final Dose + 30 days': This period is defined as the time-period between the date and time of initial dose of study edoxaban or study VKA and the date and time of final dose of study edoxaban or study VKA plus 30 days, including study regimen interruptions.

Follow-up is censored at the last date of known follow-up status in subjects with incomplete follow-up. Investigators are instructed to complete follow-up as much as possible irrespective of changes or discontinuation of study medication.

When using the ITT analysis set, the reference date is the date and time of randomization, whereas in mITT and PP analyses, the reference date is the date and time of first intake of study edoxaban or study VKA.

The main analyses of adjudicated primary and secondary exploratory endpoints (Section 7.1 and 7.2, respectively) will be based on ITT analysis set and takes the first adjudicated event during the 'overall study period' into account.

However, in supplemental analyses, other combinations of analysis sets and analysis periods may be considered to evaluate the robustness of the main analyses on adjudicated safety or efficacy endpoints. Details on these analyses will be described in the SAP.

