9.4. Timing of Adverse Event Reporting

All AEs must be recorded and reported from the stated starting point of the clinical trial (immediately after signing IC) including AEs taking place during the administration of other drugs. Even if the subject has not yet received the investigational study regimens, untoward medical occurrences have to be treated as AEs.

The period of AE reporting is defined as follows:

AEs that occur within 30 days after the last dose of the assigned study anticoagulant-based regimen which are reported to the Investigator (regardless of the date of a follow-up visit) must be recorded in the eCRF.

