11.5. Safety Analyses

11.5.1. Adverse Event Analyses

Adverse events meeting the criteria defined in Section 9.1 will be recorded in the eCRF and coded by system organ class and preferred term using the Medical Dictionary for Regulatory Activities (MedDRA), version 19.1 or newer.

Treatment-emergent adverse events (TEAEs) are defined as events which start on or after any first dose of the assigned study medication regimen or started prior to but then worsened after any first dose of the assigned study medication regimen. An AE that occurs more than 30 days after the date of the last dose of the assigned study medication regimen will not be counted as a TEAE.

The AE analysis will be based on the SAF analysis set. TEAEs will be summarized by treatment group. The incidence of TEAEs will be presented by treatment group, by relationship to the assigned study regimen, and by severity. If more than one AE is coded to the same preferred term for the same subject, the subject will be counted only once for that preferred term using the greatest severity and strictest causality for the summarization by severity and causal relationship. Frequent TEAE (reported by at least 5% resp. 1% of subjects in any treatment group) will be summarized by regimen group.

The incidence of death, SAEs, drug-related SAEs, and AEs leading to permanent discontinuation of the assigned study regimen will be summarized. All AEs meeting the criteria defined in Section 9.1 will be included in a data listing and a listing to display the coding of AEs will be prepared as well.

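### TEAE percentages use all treated subjects as denominator but stop counting 30 days after the last dose, so unequal discontinuation between arms distorts the crude comparison

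*Combined protocol and SAP*

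**What the plan says.** - **Denominator.** Section 11.2, General Statistical Considerations: "For AE and incidence based analyses, percentages will be based on the total number of subjects in the analysis set of interest", taken separately for each regimen.
- **Analysis set and measure.** Section 11.5.1, Adverse Event Analyses: "The AE analysis will be based on the SAF analysis set", and "The incidence of TEAEs will be presented by treatment group, by relationship to the assigned study regimen, and by severity".
- **End of counting.** Section 11.5.1: an AE occurring "more than 30 days after the date of the last dose of the assigned study medication regimen will not be counted as a TEAE".
- **Reporting period.** Section 9.4 requires recording of "AEs that occur within 30 days after the last dose of the assigned study anticoagulant-based regimen which are reported to the Investigator". Section 9.5.1 uses the same 30-day limit.
- **Exposure.** Section 11.3 summarises exposure, interruptions and permanent discontinuations by arm, descriptively and separately from the AE tables.
- **Adjudicated endpoints.** Section 11.4 uses a Cox model with censoring. Sections 11.4.1 and 11.4.2 take the ITT set to Day 365 as the main analysis and also present results from initial dose to final dose plus 30 days.

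The text provides no person-time rate, time-to-first-event analysis or common 12-month summary for adverse events.

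**The concern.** Time at risk for a TEAE is determined after randomization, because it depends on when the subject stops treatment. The trial is open-label and compares regimens with different drugs, so stopping may well differ by arm. A percentage of all treated subjects takes no account of this. With the same underlying hazard in both arms, the arm that stops sooner shows the lower percentage. At stake is the reading of the TEAE and SAE tables, where a regimen could look slightly better partly because its subjects were observed for less time.

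**Working it through.** **Inputs from the plan.** The denominator is all SAF subjects in the arm (11.2, 11.5.1). Counting ends at last dose + 30 days (11.5.1). Planned treatment is 12 months (5.7), so a completer has a window of about 13 months. The plan states no TEAE incidence and no discontinuation rate, so there is no figure of its own to reproduce.

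**Assumptions.** The AE hazard λ is constant and identical in both arms. A fraction d of an arm stops at month m, independently of AEs. The remainder complete treatment.

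**Formula.** Crude incidence = (1 − d)·(1 − e^(−13λ)) + d·(1 − e^(−(m+1)λ)), with λ per month.

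**Worked case.** Take 5 first events per 100 subject-years (λ = 0.05/12) and m = 3. Then 1 − e^(−13λ) = 0.05273 and 1 − e^(−4λ) = 0.01653.
- Arm A, d = 0.12: 0.88 × 0.05273 + 0.12 × 0.01653 = 4.84%.
- Arm B, d = 0.24: 0.76 × 0.05273 + 0.24 × 0.01653 = 4.40%.
- Ratio A/B = 1.099, although the true ratio is 1.

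| Stopping, A vs B | Crude %, A vs B | Ratio A/B | Mean window in months, A vs B |
|---|---|---|---|
| 12% vs 24% at month 3 | 4.84 vs 4.40 | 1.099 | 11.92 vs 10.84 |
| 15% vs 25% at month 4 | 4.79 vs 4.47 | 1.072 | 11.80 vs 11.00 |
| 15% vs 20% at month 4 | 4.79 vs 4.63 | 1.035 | 11.80 vs 11.40 |

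For an event with a 50% yearly risk the three ratios are 1.086, 1.060 and 1.029, so the size depends little on how common the event is. With equal d the ratio is 1. Under these assumptions a first-event rate per subject-year over the same window gives a ratio of 1.00.

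**Sensitivity to early clustering.** Events after PCI may be concentrated early. Assume a 20% yearly risk, half the yearly hazard in the first 30 days, equal hazards in both arms, and exponential discontinuation reaching 10% (A) vs 30% (B) by 12 months.
- n/N: 20.28% vs 19.20%, ratio A/B = 1.057. With a constant hazard it would be 20.49% vs 18.44%, ratio 1.111, so clustering roughly halves the distortion.
- Rate: mean subject-years to first event or end of window are 0.878 vs 0.789, giving 23.1 vs 24.3 per 100 subject-years, ratio A/B = 0.949.

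The simple rate is then wrong by about as much as the percentage, in the opposite direction. A Cox model censored at the end of the window compares hazards at the same time since first dose. In this scenario it targets a hazard ratio of 1 without needing a constant hazard.

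**The case against.** **What stands.**
- The main safety outcomes are not touched. MCRB, major bleeding, any bleeding and symptomatic intracranial hemorrhage (7.1, 7.2) are adjudicated and analysed by Cox model on the ITT set to Day 365. A reader might infer that the trial's safety conclusion is biased; the documents do not support that.
- A reader might extend the point to deaths. Death from any cause is adjudicated (17.1.2) and enters a composite analysed to Day 365, with single components explored (7.2, 11.4.2).
- A reader might extend it to AEs leading to discontinuation. Those events end treatment themselves and so fall inside the window. They also partly offset the effect in the overall TEAE count.
- Sections 5.7 and 5.10.1 might seem to support a shorter window in one arm. They do not. An interruption with later resumption does not bring the last dose forward. Under 5.7, the other drugs continue when a single one is refused, which may lengthen the window.
- The effect is small beside sampling error. With 750 per arm, 4.84% vs 4.40% is about 36 vs 33 subjects, and the 95% half-width of the difference is about 2.1 percentage points. No formal test of TEAEs is planned, and readers will see exposure by arm.

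**What stands in part.**
- The sentence in 11.5.1 on deaths and SAEs does not repeat the treatment-emergent restriction. For SAEs the cut-off comes from the reporting period in 9.4 and 9.5.1. Visits to 12 months ask for all AEs since the last visit (6.2.1, 6.2.3), so some later SAEs may be recorded.
- The Synopsis defers all analysis details to an SAP, and the supplied document contains no separate SAP text. Rates could be specified there. But 11.2 fixes the denominator, and 11.5.1, unlike 11.5.2 and 11.5.4, does not refer to the SAP.

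**Conclusion.** The point holds for non-adjudicated TEAEs and treatment-emergent SAEs only. If discontinuation differs by arm, crude percentages favour the arm that stops sooner. The size is about 3 to 10% relative for 15% vs 20% up to 12% vs 24% stopping at 3 to 4 months. This assumes equal hazards and stopping unrelated to AEs. It is less with early clustering and zero with equal discontinuation. Because the stopping rates are assumptions, the documents do not show which arm would benefit. A reader might also infer that rates should replace the percentages as the basis for comparison. The early-clustering check shows that this would exchange one distortion for another of similar size. This is a cheap improvement, not a flaw in the primary analysis.

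**What to change.** In Section 11.5.1:
1. Keep n (%). For overall TEAEs, SAEs and frequent TEAEs, add subject-years at risk per arm and first-event rates per 100 subject-years with 95% CI. Time runs from first dose to the first event or the end of the 30-day window.
2. For overall TEAEs and SAEs, also give the Kaplan-Meier cumulative incidence and a Cox hazard ratio, both censored at the end of that window. The plan already applies the Cox model to adjudicated endpoints over initial dose to final dose plus 30 days. Kaplan-Meier is currently specified only for the period to Day 365, so that part is an extension.
3. State which last dose closes the window. Section 9.4 ("AEs that occur within 30 days after the last dose of the assigned study anticoagulant-based regimen") can be read as the last anticoagulant dose. Section 11.5.1 ("An AE that occurs more than 30 days after the date of the last dose of the assigned study medication regimen") can be read as the last dose of any component. The two differ when one drug is stopped and others continue, and any time at risk depends on the choice.

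The cost is SAP wording and table programming. Study medication start and stop dates are already captured in the eCRF (5.7). The simple rates assume a roughly constant hazard, so they supplement n (%) and do not replace it. The censored estimates describe the treatment window and assume that stopping is not informative.

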11.3. Study Population Data

Subject disposition will be summarized for each randomized treatment regimen and in total for the ITT analysis set. The number of subjects for each defined analysis set by treatment regimen will also be tabulated.

The demographic and baseline characteristics including baseline disease status will be summarized descriptively by treatment regimen for the ITT, mITT, PP and SAF analysis sets.

Exposure to study medication (edoxaban, VKA, P2Y12 antagonist, and ASA) will be summarized using descriptive statistics by treatment regimen for the mITT, PP and SAF analysis sets. Interruptions and permanent discontinuations (see Section 5.7) will be summarized by treatment group for the same analysis sets.

The time in therapeutic range (TTR) (INR: 2.0 to 3.0, inclusive) will be estimated for each subject randomized to the VKA-based antithrombotic regimen using the interpolation method of Rosendaal (26).

11.4. Statistical Analysis

For each of the primary and secondary exploratory endpoints, appropriate summary statistics (e.g. event rate) including 95% CI will be provided.

For each of the endpoints, the time from reference date to the first occurrence of an event (based on CEC adjudication), is analyzed using a Cox proportional hazard model with treatment regimen as a factor and all the stratification factors from the randomization (IXRS) as covariates, to provide point estimates and 95% Confidence Interval (CI) for the hazard ratio (HR). Depending on the analysis period used in the statistical analysis, subjects without an occurrence of an event will be censored at the last date of the analysis period or at the last date of known outcomes status. The latter is determined on an individual basis for subjects with incomplete follow-up.

The parameter estimate β (= \ln (Hazard ratio)), its standard error, p-value, and 95% Confidence Limits are calculated according to the maximum partial likelihood method (ML), with Breslow's approximation for ties (SAS PHREG procedure).

For time to first event analyses based on the 'overall study period', cumulative event rates over time are summarized using the Kaplan-Meier method.

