2. STUDY OBJECTIVES AND HYPOTHESES

2.1. Study Objectives

2.1.1. Primary Objectives

The primary objective is to compare a 12-month antithrombotic regimen of edoxaban in combination with clopidogrel or another P2Y₁₂ antagonist and at least 1-month ASA in subjects with AF following successful PCI with stent placement in terms of the incidence of major or clinically relevant non-major ISTH-defined bleeding (MCRB).

There are two primary hypotheses for bleeding to be tested in this study.

- The edoxaban-based antithrombotic regimen is non-inferior to the VKA-based antithrombotic regimen with regards to MCRB.
- The edoxaban-based antithrombotic regimen is superior to the VKA-based antithrombotic regimen with regards to MCRB.

These two hypotheses are tested in a hierarchical manner, non-inferiority followed by superiority to control the type-I error rate, with adequate power for each of the two hypotheses.

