5.2.2. VKA-based regimen for 12 months (control regimen)

- Oral VKA of choice with dosing for target international normalized ratio (INR) between 2.0 - 3.0, inclusive.
- Clopidogrel 75mg once-daily (or in the presence of a documented clinical need prasugrel [10 mg once-daily]/ ticagrelor [90 mg twice-daily] may be used).
- ASA (100 mg once-daily) for a minimum of 1 month and up to 12 months duration at the Investigator discretion guided by the clinical presentation

(ACS or stable CAD), and upon the CHA2DS2-VASc and HAS-BLED score (1).

- The use of a P2Y₁₂ antagonist other than clopidogrel must be pre-declared, together with the intended duration of ASA treatment.

For simplicity, this protocol uses the term "edoxaban" to refer to edoxaban tosylate, "clopidogrel" to refer to clopidogrel bisulfate and the term "prasugrel" to refer to prasugrel hydrochloride.

Pre-declaration means that the Investigator specifies this information in the IXRS, prior to randomization and assignment to an antithrombotic regimen.

3. Edoxaban

Edoxaban tosylate (DU-176b, trade names Lixiana®, Savaysa®), referred throughout this protocol by the term "edoxaban" for simplicity, is part of the edoxaban-based regimen. Please refer to Section 5.9 Labeling and Packaging.

According to local SmPC or 1B as applicable, subjects may take edoxaban with or without food, in the morning or evening, but at approximately the same time every day.

If a dose of edoxaban is missed, the dose must be taken as soon as possible as long as on the same day. The dose of edoxaban must not be doubled to make up for a missed dose.

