11.4.1.1. Test for non-inferiority

The *primary analysis to show non-inferiority* will be based on first occurrence of an (adjudicated) MCRB that occurred during the 'overall study period' for all subjects belonging to the ITT analysis set and applying the aforementioned statistical method. The edoxaban-based regimen will be considered non-inferior to the VKA-based regimen, if the upper boundary of the two-sided 95% CI for HR falls below 1.20.

To evaluate the robustness of the primary analysis, the analysis will be repeated using the mITT and PP analysis set. In addition, the statistical results based on the following analysis periods: 'initial dose to final dose+ 30 days', 'overall study period+ 30 days' will be presented but should be interpreted in a more descriptive way. Results for other combinations of analysis sets and analysis periods may be presented if considered necessary.

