11.4.1.2. Test for superiority

The *primary analysis to show superiority* will be based on first occurrence of an (adjudicated) MCRB that occurred during the 'overall study period' for all subjects belonging to the ITT analysis set and applying the aforementioned statistical method. The edoxaban-based regimen will be compared with the VKA-based regimen for superiority only if the non-inferiority of the edoxaban based regimen is established first. The edoxaban-based regimen will be considered superior to the VKA-based regimen, if the upper boundary of the two-sided 95% CI for HR falls below 1.00.

To evaluate the robustness of the primary analysis, the analysis will be repeated using the mITT and PP analysis set. In addition, the statistical results based on the following analysis periods: 'initial dose to final dose + 30 days', 'overall study period + 30 days' will be presented but should be interpreted in a more descriptive way. Results for other combinations of analysis sets and analysis periods may be presented if considered necessary.

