11.9. Sample Size Determination

The sample size determination for the study was driven by requirements for testing superiority of the edoxaban-based regimen over the VKA-based regimen as described above.

The power calculation was based on a test using the Cox proportional hazards model and was performed with PASS version 14.0.4, with the module for two survival curves using Cox's proportional hazards model) under the ITT principle with a fixed follow-up time of 12 months (i.e., 365 days).

Based on a review of available safety data, the estimated one-year event rate of the primary endpoint (MCRB, i.e. ISTH major or clinically relevant non-major bleeding) under the VKA-based antithrombotic regimen is 24%-(13, 27, 28). The edoxaban-based antithrombotic regimen is anticipated to reduce the one-year incidence to 18% (a relative risk (RR) of 0.75). Under the assumption of an exponential distribution, the hazard ratio (HR) equals 0.7231.

The accrual of 2 x 712 evaluable subjects provides 80% power to demonstrate superiority of the edoxaban-based antithrombotic regimen over the VKA-based

antithrombotic regimen at a two-sided $\alpha=0.05$. To compensate for loss-to-follow-up within 12 months, the final sample size is set at 2 x 750 subjects.

With this sample size, the study has 82% power to show non-inferiority (with a margin of 1.20) if the underlying HR is 0.88 at a one-sided significance level of 2.5%.

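### Does the undefined event rate in Section 11.4 leave the primary bleeding comparison at odds with an objective worded as incidence?

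*Combined protocol and SAP*

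**What the plan says.** The primary objective (Section 2.1.1) compares the regimens "in terms of the incidence of major or clinically relevant non-major ISTH-defined bleeding (MCRB". Section 7.1 defines the primary endpoint as a time to first event.

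Section 11.4 makes three statements about results for each endpoint:

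- Descriptively, "appropriate summary statistics (e.g. event rate) including 95% CI will be provided".
- Between arms, a Cox model with treatment and the randomization strata gives a hazard ratio with 95% CI.
- For the overall study period, which Section 11.2 ends at Day 365, "cumulative event rates over time are summarized using the Kaplan-Meier method".

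Both decisions rest on the hazard ratio. Non-inferiority is met "if the upper boundary of the two-sided 95% CI for HR falls below 1.20" (Section 11.4.1.1), and superiority "if the upper boundary of the two-sided 95% CI for HR falls below 1.00" (Section 11.4.1.2).

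Section 11.9 takes a one-year rate of 24% on the VKA-based regimen, which the edoxaban-based regimen is "anticipated to reduce the one-year incidence to 18% (a relative risk (RR) of 0.75". It turns these into a hazard ratio of 0.7231 under exponential survival and powers a Cox test. Section 11.2 adds a general table convention: "For AE and incidence based analyses, percentages will be based on the total number of subjects in the analysis set of interest". The synopsis leaves the analysis details to a separate SAP, which is not part of the text reviewed here.

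**The concern.** The objective is worded as incidence and the planning case as one-year risks, yet the only named contrast is a hazard ratio. The one promise of an absolute figure with an interval leaves that figure open. It could be a crude share of randomized subjects, a rate per person-year, or the Kaplan-Meier estimate at Day 365. The documents give some support to more than one reading: Section 11.9 uses the term for a cumulative one-year risk, and Section 11.2 bases incidence percentages on everyone in the analysis set.

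At stake would be the absolute result that readers set beside the planned 24% and 18%. If the three readings diverged materially, the choice could be made after seeing the data. A crude share also shifts when follow-up is lost unequally, which is conceivable in an open-label trial.

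**Working it through.** **1. Is the sample size on the incidence scale?**

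Inputs from Section 11.9: 24% and 18% at one year, two-sided alpha 0.05, power 80%, 712 evaluable per arm.

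- Hazard ratio: ln(0.82)/ln(0.76) = 0.1985/0.2744 = 0.7231, as stated.
- Events (Schoenfeld): 4(1.960 + 0.842)²/(ln 0.7231)² = 298.7, so 299.
- Subjects: mean event probability (0.24 + 0.18)/2 = 0.21; 299/0.21 = 1,424, or 712 per arm, as stated.
- A two-proportion test on 24% vs 18% would need 723 per arm, or 756 with continuity correction.

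The stated 712 is therefore the Cox figure. The percentages are inputs to it.

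**2. Is the non-inferiority power on the same scale?**

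- At a hazard ratio of 0.88 the edoxaban risk is 1 − 0.76^0.88 = 21.46%.
- Expected events among 1,500: 1,500 × (0.24 + 0.2146)/2 = 341.
- Power: Φ(½√341 × ln(1.20/0.88) − 1.96) = Φ(0.90) = 81.7%, against 82% stated.

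Sizing, margin, test and decision rule agree.

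**3. How far apart are the readings of the event rate?**

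Take the planning rates with 38/750 = 5.07% lost per arm. That loss is implied by the step from 712 to 750; Section 11.9 states no rate. With yearly hazard l and loss hazard d = −ln(1 − loss), the crude share is l/(l + d) × (1 − exp(−(l + d))).

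| Reading | VKA | Edoxaban | Difference |
|---|---|---|---|
| Kaplan-Meier, Day 365 | 24.0% | 18.0% | −6.0 points |
| Crude events/N | 23.41% | 17.56% | −5.86 points |
| Per 100 person-years | 27.4 | 19.8 | −7.6 |

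Crude and Kaplan-Meier differ by 6.0 − 5.86 = 0.14 points. The 95% half-width of the difference at 750 per arm is 1.96 × √[(0.24 × 0.76 + 0.18 × 0.82)/750] = 4.11 points. The person-year figure is in another unit and would be labelled as such.

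**4. Unequal loss (assumed, not from the documents).**

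- 8% lost on VKA and 2% on edoxaban: crude 23.07% vs 17.83%, difference −5.25 (from unrounded values).
- 2% and 8%: 23.77% vs 17.29%, difference −6.48.

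The shift from −6.0 is 0.75 or 0.48 points, still well inside the interval. Kaplan-Meier stays at −6.0 only if loss is unrelated to bleeding risk.

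**5. Would fixing Kaplan-Meier remove all error?**

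Kaplan-Meier censors deaths without bleeding. Using the same formula with deaths in place of loss, 3% mortality (assumed) gives true shares of 23.65% and 17.74%, and 6% gives 23.31% and 17.47%. Kaplan-Meier would then read about 0.3 to 0.7 points above the share who bled, and the difference would be 0.1 to 0.2 points too large. The crude share understates the arms by 24.0 − 23.41 = 0.59 and 18.0 − 17.56 = 0.44 points. The two departures are of similar size.

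**The case for a change.** The best case for acting is that the wording is open and closing it is almost free. One sentence and one table row would tie the event rate to Kaplan-Meier at Day 365 and add a difference with its interval, without touching alpha, power, margin or decision rule. Only that measure matches the one-year quantity in Section 11.9 while allowing for censoring without assuming a constant hazard. Naming it in advance also removes a choice after the fact.

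Part of this stands. Section 11.4 does not expressly link the event rate to the Kaplan-Meier curves, states no interval for the curves, and names no Day 365 difference between arms.

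The rest is weaker. The section already plans cumulative rates by Kaplan-Meier over the period that ends at Day 365, and Section 11.9 uses the term for a cumulative one-year risk, so the natural reading is available. The all-subjects denominator in Section 11.2 belongs to a paragraph on categorical variables; the same section has subjects without the endpoint censored. Follow-up is to continue for 12 months whatever happens to treatment (Sections 5.7, 6.4 and 6.5), which limits loss. An added risk difference would be descriptive, and whether to show it is a reporting preference.

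**Conclusion.** No change to the plan is needed. Testing an incidence objective with a time-to-first-event hazard ratio over fixed follow-up is not a contradiction, and the sample size reproduces as a Cox calculation. The open point is which descriptive rate accompanies the hazard ratio. An analyst writing the SAP would ordinarily take the Kaplan-Meier estimate at Day 365 with its interval, and that document may already say so.

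Under the planning rates and the implied 5.07% loss, the choice between crude and Kaplan-Meier moves the difference by 0.14 points against an interval of about ±4.1. Under the assumed 2% and 8% losses it moves by up to about 0.75 points. These figures assume exponential event times and loss that is non-informative within each arm. Neither non-inferiority nor superiority depends on the choice.
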